Participants randomized to ADAPT will be actively involved in the study for a ~10 week period (from screening to post assessment). Those who are randomized to the waitlist control and then opt to receive ADAPT afterwards will be involved for ~16 weeks.

It is anticipated that we will be actively enrolling participants for 2 years. After study completion, three additional months will be allotted for data analysis.

- **Description of intervention and administration.** In this study, a psychological intervention, Aim to Decrease Anxiety and Pain Treatment (ADAPT), was developed and will integrate mindfulness meditation with cognitive behavioral therapy approaches for managing pain and anxiety to improve patient outcomes. ADAPT is an individual therapy with caregiver involvement that consists of 2 interactive sessions with a psychological provider (60 minutes) once per week for the first two weeks, followed by 4 weeks of self-paced web modules (45 minutes per week) in conjunction with interventionist support (15 minutes per week). Participants will complete the ADAPT program virtually (e.g., using HIPPA compliant videoconferencing or phone). The duration of ADAPT is 6 weeks, although up to eight weeks will be permitted to account for scheduling conflicts and participant illness. Preliminary testing has shown that ADAPT successfully reduces pain and anxiety over time.

Participants randomized to ADAPT will be actively involved in the study for a ~10 week period (from screening to post assessment). Those who are randomized to the waitlist control and then opt to receive ADAPT afterwards will be involved for ~16 weeks.

- **Randomization, blinding:** Participants will then be randomized to either ADAPT or waitlist control. Gender and age will be used as blocking variables in randomization. For further detail on randomization, see 9.2 *Sample Size and Randomization*. The PI ([name]), data analyst ([name]), and outcome assessors (post-baccalaureate research coordinator) will be blinded to intervention group assignment. The study statistician ([name]), PI ([name]), and mentorship team ([name] and [name]) will be blinded to the primary mechanistic outcome measure. For further detail on blinding, see 6.2.3 *Blinding*.

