**Table 1. Blinding of Study Personnel.**

Stake holder	Intervention group assignment	Primary Mechanistic Outcome Measure	Clinical/ Functional Outcome Measure
Study subjects	Subjects will be aware if they are randomized to ADAPT versus waitlist.	The subjects will participate in the collection of this data but will not be involved in the interpretation of the data or the analysis of the results.	Subjects will provide such data. As such, they will be aware of their own responses on clinical/functional outcome measures.
Interventionists licensed clinical psychologist ([name]), backup interventionist	The interventionist will know if participants are randomized to the intervention group.	The interventionist will not be involved in analyses.	The interventionist will not be involved in analyses.
Outcome Assessors (post-baccalaureate research coordinator)	Outcome assessors will be blinded as to group assignment.	The outcome assessor will be involved in the collection of such data, but will not be involved in the interpretation and analysis of results.	The study coordinator will serve as an outcome assessor. However, data will be collected directly from participants using online forms. In addition, the study coordinator will only access/manage post-assessment data that has been de-identified (with group assignment removed).
Data Analysts/Statistician ([name])	The study statistician will be blinded to the group assignment.	The study statistician will be blinded until the completion of this study	The study statistician will generate reports and submit data as requested by NCCIH or the IMC

			for the duration of the study.
Principal Investigator ([name]) and Study Mentors ([name], [name])	The PI will be blinded to intervention group assignment.	The PI and her mentorship team will be blinded to post-assessment data results until after the completion of the analysis. She will participate in processing/management of fMRI data without knowledge of group assignment.	The PI and her mentorship team will be blinded to post-assessment results by group assignment until after completion of the analyses.

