### Treatment Assignment Procedures

Randomization will be generated using PROC PLAN in SAS 9.3 by a biostatistician who is part of the University of Cincinnati's Center for Clinical and Translational Science and Training (CCTST). The CCTST biostatistician will not have access to the data. This data management support service will generate randomization and will assign a Treatment A/Treatment B designation. The randomization schedule and code sheet will be held confidentially by a senior Clinical Research Manager in the study mentor's ([name]) lab, and the study

interventionist ([name]) will contact the Clinical Research Manager to get the next assignment when a participant is enrolled in the study.

Gender and age will be used as blocking variables in randomization. Specifically, there will be four randomization tables for gender (male and female) by age (younger i.e., 11-13 years of age and older i.e., 14-16 years of age) combination:

- $11 \leq \text{Age} < 14$ , Female
- $14 \leq \text{Age} < 17$ , Female
- $11 \leq \text{Age} < 14$ , Male
- $14 \leq \text{Age} < 17$ , Male

Patients will be randomized to either ADAPT or WL. A separate randomization list will be produced for each of the four (4) blocks – Age x Sex. Per study protocol, a list of 10 treatment / control assignments will be produced per group. Within each group, a completely randomized design will be applied to allocate ADAPT or WL.

The test randomization and final randomization will require four seed numbers, one for each block size. The seed numbers below are for illustration only and will not be used.

- $11 \leq \text{Age} < 14$ , Female: Seed = 111111
- $14 \leq \text{Age} < 17$ , Female: Seed = 222222
- $11 \leq \text{Age} < 14$ , Male: Seed = 333333
- $14 \leq \text{Age} < 17$ , Male: Seed = 444444

The independent statistician will select seed numbers and will not share those final seed numbers with the project statistician ([name]) nor other members of the project team. The randomization identification number (rand\_id) will be comprised of 4 digits. The first digit will correspond to the blocks and the remaining 3 digits will be in sequential order, as listed below.

- Block 1:  $11 \leq \text{Age} < 14$ , Female. ID numbers 1001-1010
- Block 2:  $14 \leq \text{Age} < 17$ , Female. ID numbers 2011-2020
- Block 3:  $11 \leq \text{Age} < 14$ , Male. ID numbers 3021-3030
- Block 4:  $14 \leq \text{Age} < 17$ , Male. ID numbers 4031-4040

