Given that other factors such as pubertal status and subjective pain levels could influence the outcome, these factors will be included in the analysis as control covariates. Each participant's exact age will be recorded at assessment allowing personnel to control for age as an additional covariate should the need become apparent during preliminary analyses.

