## **9.6 Data Analyses**

For fMRI analysis, image processing and data analysis will be accomplished by FSL software. Each subject's functional images will be registered to their structural data using a six-parameter linear 3D transformation and then nonlinearly warped to standard space (MNI152). Analyses of both BOLD and ASL data will be accomplished via mixed effects ANOVAs. Data will be coded prior to analysis to conceal patient status to ensure blinding.

Clusters of activation will be identified using a threshold of  $Z > 3.1$  and statistical significance will be estimated according to Gaussian random field theory. Functional connectivity analysis will be conducted (Aim 1) to identify changes in functional connectivity between the AMY-PFC in ADAPT completers vs. those in the waitlist condition. A seed to whole brain analytic approach will be used to identify any/all differences observed. Pain-related brain activations are expected to diminish for those that complete ADAPT compared to the waitlist condition (Aim 2). For the exploratory aim, mechanisms associated with a positive treatment response (decreased pain intensity/ unpleasantness/ anxiety during WL-SPT) after ADAPT will be identified. Normalization of abnormal connectivity patterns are predicted to categorize changes in pain and anxiety. Specifically, decreases in brain activations and reductions in functional connectivity will be examined in relation to improvements in pain and anxiety post treatment using multiple (linear) regression.

While all efforts will be made to minimize missing data through the use of electronic data capture and real-time adherence data collection, missing data is still inevitable in RCTs. Thus, we will employ several strategies to handle missing data with specific attention on how to handle missing not-at-random. Specifically,

missing data will be handled via ML estimation with auxiliary correlate inclusion (e.g., Graham, 2003; Enders, 2010). Missing not at random will be addressed with mixture MNAR methods (e.g., Gottfredson, Bauer, & Baldwin, 2014; Muthen, et al., 2011; Sterba & Gottfredson, 2015).

Given that other factors such as pubertal status and subjective pain levels could influence the outcome, these factors will be included in the analysis as control covariates. Each participant's exact age will be recorded at assessment allowing personnel to control for age as an additional covariate should the need become apparent during preliminary analyses.

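### Randomisation uses four sex-by-age lists, but neither factor is written into the analysis model and exact age enters only on an undefined trigger (minor)

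*Combined protocol and SAP*

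**What the plan says.** Section 9.2, Treatment Assignment Procedures: "Gender and age will be used as blocking variables in randomization". The strata are female or male by 11-13 or 14-16 years, and "A separate randomization list will be produced for each of the four (4) blocks", with 10 assignments each. Allocation within a list is described as completely randomised; an equal split is not stated.

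Section 9.6 gives the model in one line: "Analyses of both BOLD and ASL data will be accomplished via mixed effects ANOVAs". No terms are listed. The covariate text follows: "Given that other factors such as pubertal status and subjective pain levels could influence the outcome, these factors will be included in the analysis". Exact age is recorded so that staff can "control for age as an additional covariate should the need become apparent during preliminary analyses". Section 9.2 carries the same covariate text. Neither place says what the preliminary analyses are, what would show a need, or who decides.

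On safeguards, Section 3 says that the statistician, the PI and the mentors "will be blinded to the primary mechanistic outcome measure". For that outcome, Table 1 in Section 6.2.3 adds: "The study statistician will be blinded until the completion of this study". The final analysis is run on Treatment A versus B, with the code revealed afterwards. Section 9.4 plans no interim analyses.

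**The concern.** A trial that randomises within strata is normally analysed with those strata, or the factors behind them, in the model. Here two analysts could follow Section 9.6 to the letter and fit different primary models: one with sex and age group as blocking terms, the other with only pubertal status and pain. A third could add exact age after a look at the data.

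Three things are at stake, all modest. The analysis may not match the randomisation. One term in the primary model depends on an unspecified inspection of data. And if each list splits evenly, leaving out factors that predict the outcome makes the test somewhat conservative.

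The same sentence has a related gap. Pubertal status and pain are measured at baseline and again at post assessment (Sections 6.2.2 and 6.2.5), but the covariates have no time point and the pain rating is not named. ADAPT is meant to lower pain, so a model adjusted for post-treatment pain would no longer estimate the total ADAPT effect.

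**Working it through.** **1. The text.** The plan states no figure on this point, so there is none to reproduce. The lists add up: 4 × 10 = 40, the N used in Section 9.2. Sections 3, 4.3 and 9.2 name gender and age as blocking variables in randomisation. Sections 9.1, 9.2 and 9.6 never carry them into a model.

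**2. Where the terms must enter.** Section 9.6 could mean a model of subject-level change images or a pre/post repeated-measures ANOVA. In the second, for subject *i* with arm *T* and covariate *x*:

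- pre = aᵢ + βxᵢ + error
- post = aᵢ + βxᵢ + τ + δTᵢ + error
- post − pre = τ + δTᵢ + error

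The βxᵢ term cancels, so main effects of sex and age cannot alter the arm-by-time estimate δ. A simulated 40-subject pre/post data set shows this. The estimate was 0.4104 (SE 0.345) with and without the main effects, and changed to 0.4029 (SE 0.351) only when sex-by-time and age-by-time were added.

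**3. Test size and power.** Inputs from the documents: N=40 and an effect of 0.4, read here as SD units (Section 9.2), and a 65/35 sex split (Section 4). Assumptions:

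- one scalar change score, not the peak-detection power of Section 9.2;
- sex and linear age sharing equally 0, 10 or 20% of the variance in change (R²), because the documents give no value;
- pubertal status correlated 0.7 with age.

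An effect of 0.9 SD is added because it gives about 80% power at this size: (1.960 + 0.842) × √(4/40) = 0.886. The plan model is arm + pubertal status + baseline pain; the alternative adds sex and continuous age. Each cell is 20,000 least-squares simulations, two-sided 5%. The Monte Carlo SE at 5% is √(0.05 × 0.95/20,000) = 0.15 points.

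Power (%) at 0.9 SD:

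| Lists | R² | Plan model | + sex, age | Change |
|---|---|---|---|---|
| Balanced, 10 each | 0 | 77.0 | 75.9 | −1.1 |
| | 10% | 78.9 | 80.5 | +1.6 |
| | 20% | 80.5 | 85.2 | +4.7 |
| Balanced, 13/13/7/7 | 0 | 77.3 | 76.3 | −1.0 |
| | 10% | 78.1 | 79.9 | +1.8 |
| | 20% | 80.4 | 85.1 | +4.7 |
| Not forced, 10 each | 0 | 75.9 | 73.1 | −2.8 |
| | 10% | 77.0 | 78.0 | +1.0 |
| | 20% | 77.6 | 82.3 | +4.7 |
| Not forced, 13/13/7/7 | 0 | 75.8 | 73.1 | −2.7 |
| | 10% | 76.3 | 77.3 | +1.0 |
| | 20% | 77.8 | 82.6 | +4.8 |

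- At R²=5%, repeat simulations gave +0.1 to +0.5 points with balanced lists and −1 to 0 without.
- At 0.4 SD, power is about 21-27% with or without the terms.
- With the four strata in place of sex and age, the change over both effect sizes is +1.1 to +4.1 points balanced and −0.8 to +2.7 not forced at R² of 10-20%. At R²=0 it is −0.3 to −1.2 and −1.2 to −4.2.
- Size of the plan model with balanced lists is 4.4% at R²=10% and 3.7-3.9% at 20%. Without forced balance it is 4.9-5.3%. With sex and age added it is 4.8-5.2% throughout.

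**4. The age option.** The plan gives no rule, so two were tried. Adding age when its own p<0.05 gives a size of 4.0-5.3% balanced and 5.1-5.5% not forced. Keeping whichever model gives the smaller arm p-value, an adverse rule, gives 4.3-5.6% and 5.9-6.0%.

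**The case against.** The strongest reply is that the plan already covers this. The phrase about other factors follows directly on the sex-by-age lists in Section 9.2, and calling exact age an additional covariate suggests that the blocking group is already in the model. That reading is open, but no section states it.

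A second reply is that blinding contains the discretion. It does reduce the risk. But A/B coding hides which arm is which, not whether A and B differ. With no interim analysis planned, the preliminary look may come after completion, when the outcome by A and B is available to the statistician. It may equally be a baseline check; the text does not say.

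A third reply is that the benefit rests on an assumed R². This stands. Pubertal status is already a committed covariate and takes up part of the age effect. If it also correlates 0.4 with sex (a further assumption), the gain at R²=10% is only +0.5 to +1.0 points balanced and −0.4 to −0.5 otherwise. At 20% it is +1.9 to +2.3 and +1.0 to +1.2. Without forced balance, checks at 10% ran from about −1 to +1. A general claim of added precision is not shown for this trial.

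A reader might also infer that the age option inflates type I error, or that the plan will adjust for post-treatment pain. The first is not supported: even the adverse rule reaches only about 6%. The second has no text behind it; the time point is simply missing.

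**Conclusion.** The gap in the text is certain, and its consequence is minor. Sex and age group define the randomisation but appear in no stated model, and exact age depends on an undefined look at the data. The grounds for acting are to match the analysis to the randomisation, to remove a data-dependent choice from the primary model and, if the lists are balanced, to avoid a size of about 3.7-4.4% at a nominal 5% (R² of 10-20%, assumed).

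Power is not a ground. At 0.9 SD the change is about +1.5 to +5 points for R² of 10-20% with balanced lists and about zero at 5%. If the factors explain little and the lists are not forced to balance, the loss is up to about 3 points (sex plus age) or 4 (four strata). The sign depends on an R² that the documents do not give. All figures are for one scalar endpoint at N=40 and illustrate the order of size only. A reader might infer that the planned analysis is invalid or that results-driven covariate selection is intended; the documents support neither.

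**What to change.** In Sections 9.2 and 9.6, replace the conditional age sentence with wording such as:

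> Every primary and secondary model of the ADAPT-versus-waitlist difference in change includes sex and age at baseline (continuous; or the four strata), set before any post-assessment data are analysed. They are entered as group-level covariates when subject-level change images are analysed, or as sex-by-time and age-by-time terms when a pre/post repeated-measures ANOVA is used.

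Delete the clause that makes age depend on preliminary analyses. In the covariate sentence, limit pubertal status and one named pain rating to their baseline values.

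The cost is wording only, since every variable is already collected. Sex plus continuous age uses 2 degrees of freedom and the four strata use 3. Age overlaps with pubertal status, and with about 0.35 × 40 = 14 boys the sex coefficient will be imprecise; neither prevents the adjustment.

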## **10. DATA COLLECTION AND QUALITY ASSURANCE**

### **10.1 Data Collection Forms**

Standardized, validated measures used in prior pediatric pain studies will be used (*6.1 Schedule of Evaluations*). These measures will be administered using the REDCap platform. Participants and caregivers will be given the option to either complete baseline and post-assessment measures during their respective baseline/post assessment visit or before this visit using their own electronic device (to reduce the length of the in-person visit). A blinded post-baccalaureate research coordinator will serve as the outcome assessor and collect data at assessment visits. Home practice during ADAPT will also be measured (online module completion). Should a randomized participant prematurely discontinue participation in the study, study measures and endpoints will continue to be collected if possible. Any concomitant interventions (i.e., medical and psychological) experienced by the participants (either allowed or prohibited) will also be assessed for and recorded at baseline and post assessments. Participants will provide the reason and duration of concomitant interventions at the baseline and post assessment visits.

To ensure confidentiality, identification numbers will be used on data collection forms in lieu of names. Regarding the use of online measures and web modules, material development will be conducted in accordance with MSU policies. Hardware for this study will be provided and maintained by MSU Informatics, which maintains a secure server for supporting projects that potentially contain protected health information (PHI) and are subsequently subject to compliance with federal and state regulations regarding data of this type. The data obtained from the web program will be stored on the server, which will be backed up regularly.

### **10.2 Data Management**

All data will be identified with ID numbers exclusively and kept in locked files in a space in the Secchia Center or on a secure computer that is designated specifically for the purposes of this project. All de-identified data (with the exception of fMRI data) will be saved into REDCap, a password-protected database. Data output will be stored on a network devoted solely to the research activities associated with MSU's Biomedical Research Informatics Core (BRIC). In order to assure the accuracy of data entry, data will be verified in real-time by study staff via database-incorporated data entry checks. Electronic data stored on MSU's network is backed up nightly. The

server is maintained and all backups are conducted by the BRIC. The fMRI data will also be stored on a secure server, backed up nightly, and will only be accessible to study staff.

## **10.3 Quality Assurance**

### **10.3.1 Training**

To ensure protocol integrity, staff training will include required human subjects training, GCP training, and study/intervention specific training. Study staff training will vary based on roles (i.e., interventionists will receive specific training on conducting the intervention from the PI).

### **10.3.2 Quality Control Committee**

N/A

### **10.3.3 Metrics**

N/A

### **10.3.4 Protocol Deviations.**

All deviations will be reported to the IRB for review. They will also be recorded using a protocol deviation form documenting a brief description of the deviation, the number of participants who experienced a given deviation, and a summary of the action taken in response to the deviation or group of similar deviations. All protocol deviations will also be documented in a protocol deviation log.

### **10.3.5 Monitoring**

The study team will have quarterly meetings to monitor the progress of the study, the integrity of the treatment, discuss the need for any protocol refinements, and conduct regular safety monitoring checks of adverse events and unanticipated problems.

## **11. PARTICIPANT RIGHTS AND CONFIDENTIALITY**

### **11.1 Institutional Review Board (IRB) Review**

This protocol and the informed assent and consent documents and any subsequent modifications will be reviewed and approved by the MSU IRB.

### **11.2 Informed Consent Forms**

A signed assent and consent form will be obtained from each participant and their legal guardian (e.g., person with power of attorney) before completing any study activities. The consent form will describe the purpose of the study, the procedures to be followed, and the risks and benefits of participation. Consent forms will be IRB-approved, and the subject is required to read and review the document or have the document read to him or her. The designee will explain the research study to the subject and answer any questions that may arise. The subject will sign the informed consent document prior to any study-related assessments or procedures. Subjects will be given the opportunity to discuss the study with their surrogates or think about it

prior to agreeing to participate. They may withdraw consent at any time throughout the course of the study. A copy of the forms will be given to the legal guardian.

All efforts will be made to ensure that youth and their families understand the study and the associated risks and benefits. Participants will have opportunities to voice questions/concerns before formally providing consent/assent. Non-English speakers or those with cognitive delays that would limit understanding of the consenting process will be excluded from participation in the study.

